4.1.5. Time to progression (TTP)

Defined as the period from first dose to PD. Rules for TTP censoring are as follows:

- If there is no tumor assessment at baseline, the date of censoring is the date of the first dose of study treatment.
- If there is no tumor assessment after baseline, the date of censoring is the date of the first dose of study treatment.
- If no RECIST 1.1 progression or death is recorded, the date of censoring is the date of the last tumor assessment.
- If subjects die before the onset of disease progression, the date of censoring will be the date of the last tumor assessment.

- If no radiological progression or death is recorded prior to initiation of subsequent therapy, the date of censoring is the date of the last tumor assessment prior to the subsequent therapy.
- If subjects miss 2 or more consecutive planned tumor assessments prior to progression or death (12 weeks within 12 months from the first dose of study treatment, 24 weeks after 12 months from the first dose of study treatment), the date of censoring will be the date of the last tumor assessment.

4.1.6. Overall survival (OS)

Defined as the period from first dose to death due to any reason. It will be censored if no death occurs.

Rules for OS censoring are as below:

- If death is not obtained, the date of censoring will be the date of the last follow-up who are known to be alive.
- If the subject withdraws from the study and the date of death is not obtained, the date of censoring will be the last date who are known to be alive.

4.1.7. 6/9/12-month overall survival rate

Defined as the survival rate at 6/9/12 months after the date of first dose, which will be based on the Kaplan-Meier estimate.

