3.2.3 Follow-up period

Follow up period is initiated when the end-of-treatment decision is made.

Within 90 days after the last dose of investigational drug, follow-up visit will be performed once every 30 days (± 7 days), the first and third follow-up must be face-to-face visit, and the required safety evaluation must be completed (see study flowchart), the second follow-up is telephone visit (only collect partial data).

After the end of the safety follow-up period, the subjects will enter survival follow-up period. Investigators must follow up subject's survival every 30 days (± 7 days), until death, lost to follow-up, termination of study by the sponsor. Investigators can inquire the subject, his/her family members or local physician via phone, collect subject's survival information (death and reason of death) and data on other tumor therapies after the end of study treatment. The data on each survival follow-up needs to be recorded in detail in the original medical record.

Subjects who end study treatment for toxicity or other reasons with no radiological progression observed still need to receive radiological evaluation according to the same frequency, until progression of disease or start of other anti-cancer therapy, the radiological evidence on PD should be obtained from such subjects as much as possible.

The subject withdrawing from study treatment should also continue the safety follow-up and survival follow-up as required by protocol. Adverse effects of the investigational drug may occur after end of treatment; safety follow-up should be conducted as far as possible. Survival is one primary endpoint in this study, the study center should do their best to obtain the survival follow-up information.

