3.2.4 Criteria for continuing treatment beyond progression

Some subjects receiving immunotherapy can still clinically benefit following radiological progression. After progression of disease as defined by RECIST v1.1, subjects meeting all of the following criteria may continue with the study treatment:

- Investigators judge continuation of study treatment meets the best benefit for the subject, and the subject does not need to start other anti-cancer therapy immediately;
- The subject can tolerate study treatment;
 - No obvious decrease in the physical performance, no obvious exacerbation in tumor related symptoms;
- The subject must sign the informed consent form before continuation of the study treatment. Possible risks, discomfort and other therapeutic choices will be described in the informed consent form;
 - The study treatment continued upon must be approved by the sponsor and principal investigator of the study.

The evaluation of clinical benefit must take clinical exacerbation, continued benefit from the treatment into consideration. It is advisable to discuss with the sponsor about the decision on post-progression continuation of treatment, as judged by investigators.

If a decision of continued study treatment is made following progression, the subject should be treated, evaluated and followed up as required in the protocol. Subjects who continue treatment after imaging progress need to assess the tumor and track each target lesion, non-target lesion, and new lesion according to protocol. The overall assessment is recorded as PD as long as the new lesion did not disappear.

If further progression occurs in the next tumor evaluation, the subject should be withdrawn from the study. The initial date of progression will be used for statistical analysis which including all progression data, regardless of the continuation of study treatment following progression.

If the subject terminates the treatment for systemic condition exacerbation and no objective evidence of disease progression is shown, the progression will be reported as systemic exacerbation. Every effort should be made to obtain the objective evidence on progression in these subjects after termination of the study (e.g., radiological confirmation).

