5.1.6. Processing of missing date and missing data

Except for special circumstances, the following rules for imputation are applicable to the absence of event date for safety data.

If the date of an event is totally absent, it will not be imputed. If the date is missing, but the year and the month are consistent with that of study treatment, it will be imputed with the date of the first dose of the investigational drug, or first day of that month for other conditions; if the date of the end day is missing, but the year and the month are consistent with that of the end of treatment, the date of the end of event will be imputed with the date of the end of study treatment, or the last day of that month for other conditions.

If the month and the date of an event are missing, but the year is consistent with that of study treatment, they will be imputed with those of the start of study treatment, or 1 Jan. for other conditions.

All the dates imputed must precede the dates of withdrawal of informed consent form, lost to follow-up or death.

Missing data on laboratory tests, ECG, and vital signs will not be imputed.

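### SAP 4.1.6 can be read to censor a withdrawn subject who is known to have died but has no death date, which would raise the primary 6-month OS rate

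*SAP*

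**What the plan says.** SAP 4.1.6 defines OS and then gives two censoring rules.

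- Definition: "Defined as the period from first dose to death due to any reason. It will be censored if no death occurs".
- Rule 1: "If death is not obtained, the date of censoring will be the date of the last follow-up who are known to be alive".
- Rule 2: "If the subject withdraws from the study and the date of death is not obtained, the date of censoring will be the last date" on which the subject was known to be alive.

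SAP 4.1.7 builds the 6-month rate on these data: "Defined as the survival rate at 6/9/12 months after the date of first dose, which will be based on the Kaplan-Meier estimate". The 6-month OS rate is one of two primary endpoints. SAP section 3 ties the claim of effectiveness to a lower 95% limit above 70%.

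On incomplete dates, SAP 5.1.6 says that "the following rules for imputation are applicable to the absence of event date for safety data", and adds: "If the date of an event is totally absent, it will not be imputed".

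Protocol 3.2.3 has survival followed every 30 days (±7 days), largely by telephone: "Investigators can inquire the subject, his/her family members or local physician via phone". It keeps subjects who stop study treatment in survival follow-up.

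**The concern.** Rule 1 is about a death that was not obtained; rule 2 is about a date of death that was not obtained. If rule 2 were meant only for withdrawn subjects with no death on record, rule 1 would already cover them, with essentially the same censoring date. What rule 2 adds, read literally, is a death whose date is missing, and it treats that subject as alive when last seen.

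At stake is a primary endpoint with a pass/fail limit. Censoring a subject because he or she died is informative: it removes events and never adds any, so the error runs one way. It also departs from Protocol 8.1, which describes the 6-month rate as the share of evaluable subjects who have not died.

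Even on the harmless reading of rule 2, the programmer has no instruction for a known death with a partial or missing date, and no OS time can be computed for that subject.

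**Working it through.** **1. The plan's own figure.** Inputs from SAP 2.3: p0 = 0.70, p1 = 0.80, one-sided 0.025, power 90%, 200 subjects, raised to 220 for 10% drop-out.

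n = [z(0.975)·√(p0·q0) + z(0.90)·√(p1·q1)]² / (p1 − p0)²
= [1.960 × 0.4583 + 1.282 × 0.4000]² / 0.10² = 199.03, so 200.

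200 × 1.10 = 220 (dividing by 0.9 would give 223). The stated size is reproduced, and N = 220 is used below.

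**2. The text.**

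| Situation | What the SAP gives |
|---|---|
| No death on record | Censor when last known alive (rule 1) |
| Withdrawn, death date missing, no death on record | Censor when last known alive (rule 2, harmless reading) |
| Withdrawn, known dead, date missing | Event under the definition; censored under rule 2 read literally |
| Not withdrawn, known dead, date partial or missing | Event under the definition; no rule for the date |

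The 5.1.6 rules do not settle the last two rows. They are for safety data, leave a wholly absent date alone, and require imputed dates to precede the date of death, so they take that date as given.

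**3. Effect of one lost death.** With complete follow-up to month 6, 44 deaths among 220 give 176/220 = 80.0%. If a death with n subjects at risk is censored just before it happens, the factor (1 − 1/n) drops out and the estimate S rises by S/(n − 1). Here n runs from 220 at the first death to 177 at the last:

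- first death: 0.80/219 = 0.37 points
- last death: 0.80/176 = 0.45 points

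That is about 0.4 points per death.

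**4. Several lost deaths, and the 70% bar.** Assumptions: N = 220, deaths spread exponentially over six months, all survivors followed past month 6, and k randomly chosen deaths censored 0 to 30 days before they occurred (mean of 300 draws). The documents give no value for k. The SAP does not name the interval for the Kaplan-Meier rate, so two are shown.

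Check for 53 deaths, k = 0: S = 167/220 = 0.7591. The Greenwood sum is 1/167 − 1/220 = 0.001443, with square root 0.0380.

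- Log-log limit: S raised to the power exp(1.96 × 0.0380/|ln S|) = 0.7591^1.310 = 0.697.
- Linear limit: 0.7591 − 1.96 × 0.7591 × 0.0380 = 0.703.

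| True deaths by month 6 | k censored | KM rate % | Log-log lower limit % | Linear lower limit % |
|---|---|---|---|---|
| 44 | 0 | 80.00 | 74.08 | 74.71 |
| 44 | 1 | 80.40 | 74.51 | 75.15 |
| 44 | 2 | 80.80 | 74.93 | 75.58 |
| 44 | 5 | 82.03 | 76.24 | 76.92 |
| 44 | 10 | 84.11 | 78.48 | 79.21 |
| 53 | 0 | 75.91 | 69.69 | 70.26 |
| 53 | 1 | 76.30 | 70.10 | 70.67 |
| 55 | 0 | 75.00 | 68.73 | 69.28 |
| 55 | 2 | 75.77 | 69.52 | 70.09 |
| 55 | 4 | 76.55 | 70.34 | 70.92 |

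At the planned 80% the limit clears 70% with or without the lost deaths. With 53 deaths, one lost death moves the log-log limit across 70%. With 55 deaths it takes two on the linear scale and at most four on the log-log scale.

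**The case against.** The best answer is that rule 2 is only loosely worded. The sentence above it says OS is censored when no death occurs, and both rules can be taken as carrying that out. Rule 2 is then routine censoring of a withdrawn subject with no death on record. This is a fair reading, and the SAP does not state that known deaths leave the event count. But the words support both readings, and one of them discards deaths from a primary endpoint.

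Other points limit the size:

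- Rule 2 reaches only subjects who withdraw from the study. A subject known alive at month 6 leaves the 6-month rate unchanged.
- Contacts every 30 days, with best efforts required because survival is a primary endpoint, should keep undated deaths few. A reader might infer that month-only dates are likely because relatives are asked by telephone; the documents do not say so.
- Under Protocol 9.2, fatal events up to 90 days after the last dose are also SAE records, to which the 5.1.6 rules could apply. Nothing says that such an imputed date feeds OS, so the gap is narrower but remains.

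Two stronger inferences are tempting. The first is that Protocol 3.2.4 enlarges the affected group, since it says: "If further progression occurs in the next tumor evaluation, the subject should be withdrawn from the study". The protocol uses withdrawal from study and from treatment loosely: 3.2.2 sends subjects who terminate the study into follow-up, and the visit schedule still asks for scans after withdrawal from the study. So this wording does not show that survival collection stops.

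The second is a large rise in false-positive risk. At a true rate of 70%, simulation with a log-log limit gives a chance of passing of 2.0% with no lost deaths and roughly 10% and 15% with six and eight. But eight is 12% of the 66 deaths expected (0.30 × 220), all placed before month 6. Spreading eight over 12 months gives 6.5%. Nothing in the documents supports counts of that order.

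**Conclusion.** The point holds as a defect of wording in a primary-endpoint rule. SAP 4.1.6 can be applied so that a withdrawn subject known to be dead, but without a death date, is censored as alive. This contradicts the section's own definition, and no OS date rule prevents it.

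The size is about 0.4 points on the 6-month OS rate per affected death. It rests on N = 220, the death falling before month 6 (so the subject was last known alive before then), and near-complete follow-up otherwise. The direction is always favourable to the drug. The number of cases is unknown and probably small. It would change the conclusion only if the lower limit falls close to 70%, where one or two deaths could be enough. The documents do not support saying that the plan definitely drops known deaths, or that the bias will be large. No sample-size figure is affected.

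**What to change.** In SAP 4.1.6:

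- State that every known death is an OS event, whatever the state of its date.
- Limit rule 2 to withdrawn subjects with no report of death.
- Pre-specify the imputation of a partial or missing death date, never earlier than the day after last known alive. One example is the later of that day and the first of the known month, or that day itself when nothing is known.
- Add a sensitivity analysis under another convention, since an early-date rule can place before month 6 a death that came after it.
- Name the confidence-interval method for the Kaplan-Meier rate, because near 70% the choice matters as much as one death does.

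Separately, reconcile the withdrawal wording in Protocol 3.2.4 with the continued survival follow-up in 3.2.3.

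The cost is a few sentences, with no new data collection and no change in sample size. The reported OS rate may come out slightly lower.

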4.1.8. Time to response (TTR)

Time to response is defined as the period from the first dose to the first documentation of CR or PR (whichever occurs first). Tumor response refers to the confirmed response. The date of response is the date of first documented response rather than the date of confirmation.

4.2. Safety Endpoints

The following safety data will be collected and summarized in accordance with the study protocol (details will be elucidated in subsections):

- Adverse events
- Laboratory test data
- Vital signs data
- Electrocardiogram (ECG)
- Physical examination

4.2.1. Adverse events

Any adverse event occurring after signing of informed consent form and enrollment into the study will be collected.

Any adverse event occurring after treatment or occurring prior to treatment but being exacerbated after treatment will be counted as treatment emergent adverse event (TEAE). The following cases include but are not limited to:

- Medical condition/diseases present before starting the investigational drug that worsen after starting study treatment.
- Any new adverse event after starting study treatment.
- Abnormal laboratory measurements or test results with clinical significance occurring after starting study treatment.

If an event occurs in non-treatment period (e.g., dose interruption period or follow-up period after treatment discontinuation), this event will still be counted as a TEAE and attributed to previous treatment.

4.2.2. Laboratory test

The laboratory test data, including hematology, blood biochemistry, and urinalysis, will be collected at the visits specified in the protocol.

4.2.3. Vital signs

Vital signs, including blood pressure, heart rate, temperature, and respiratory rate, will be collected at the predefined time points in the protocol.

4.2.4. Electrocardiogram

Heart rate, PR, QT, and QTc will be collected at the predefined time points in the protocol.

4.2.5. Physical examination

Physical examination includes general condition, head, heart, lungs, abdomen, four limbs, skin, mucosa, lymph node, among others. These data will be collected at the visits/time points specified in the protocol.

4.2.6. Other safety endpoints

Other safety data to be collected according to the protocol

4.3. Pharmacokinetic Endpoints

None.

4.4. Pharmacodynamics Endpoints

None.

4.5. Other Endpoints

PD-L1 expression level ($< 1\%$ or $\geq 1\%$, based on staining percentage). It will be used to explore the relationship with the efficacy (ORR and 6-month OS%). The efficacy in subjects with PD-L1 expression level $< 1\%$ or $\geq 1\%$ will be tabulated.

5. STATISTICAL ANALYSIS

5.1. General Considerations

5.1.1. Analysis sets

Full analysis set (FAS)

Full analysis set includes all the randomized subjects who have received at least one dose of the investigational drug. Based on the analysis in the FAS, subjects belong to their allocated group as randomized rather than the actual medication group.

Per-protocol set (PPS)

It is a subset of the FAS. The PPS forms by excluding subjects with protocol deviation that has important effect on the study results from the FAS. Analysis based on the PPS, as supportive analysis, will be used as a supplement to the analysis based on the FAS. The PPS must be determined by the medical team and the statistical team of the project prior to database lock for the final analysis. All protocol deviations, including those that are judged to have major effect on the study results, will be presented in study report in a form of listing.

Evaluable set (ES)

Evaluable set is also a subset of the FAS and defined as the subjects with at least one post-baseline tumor evaluation in the FAS.

Safety set (SS)

Safety set includes all the subjects who have received at least one dose of the investigational drug. Based on the analysis in SS, subjects belong to the actual medication group (as treated). The safety set is the primary set for the safety analyses.

PD-L1 set (PD-L1)

PD-L1 set of this study comprises of all subjects who have been randomized and have received at least one dose of the investigational drug, and have provided tumor biopsy samples.

Table 1. Correspondence between study endpoints and analysis sets

Endpoints	Analysis Sets				
	FAS	PPS	ES	SS	PD-L1
ORR (%)	X	X	X		X
6/9/12-month OS rate (%)	X	X			X
TTP (months)	X				
PFS (months)	X				
DoR (months)	X				
DCR (%)	X	X	X		
OS (months)	X				
TTR (months)	X				
Safety (AE, LAB, VS, ECG, PE)				X	

5.1.2. General rule and analysis

Baseline

Unless otherwise specified, the "baseline" in this study is defined as the last non-missing measurement prior to the first dose of the investigational drug, including the measurement on the day of the first dose, but prior to the first dose.

Study days

Study days for examinations or events will be calculated using following formulas:

If the date of examination/event is before the date of first dose, study days = date of examination – date of first dose;

If the date of examination/event is on or after the date of first dose, study days = date of examination – date of first dose + 1.

General analysis

Unless otherwise specified, the following descriptive statistical summaries will be provided by the type of variables:

- The continuous variables will be summarized by mean, standard deviation, median, maximum, and minimum.
- The categorical variables will be summarized by frequency and percentage.

For time-event data, Kaplan-Meier method is used to estimate the median time of survival function and event occurrence, and the survival curve will be plotted.

Decimal places

Unless otherwise specified, the decimal places in study report will be presented using the following rules:

The decimal places of minimum and maximum will be kept consistent with that of the original data to be collected, those of mean and median will be kept one more place than the original data, and that of standard deviation will be kept two places more than the original data; however, at most 4 decimal places will be reserved.

Percentages will be presented with 2 decimal places of precision. If the frequency is 0, no percentage will be shown.

Four decimal places will be reserved for P value. If the P value is < 0.0001 , it will be presented as " < 0.0001 ", and if the P value is > 0.9999 , it will be presented as " > 0.9999 ".

If there is decimal for 95% CI, at least two and at most four decimal places will be reserved.

Analysis software

All the statistical analyses will be performed using statistical analysis software SAS[®] v9.4 or later version.

5.1.3. Derived variables

SHR-1210-Q2W group:

Duration of exposure (days) = date of last dose + 14 – date of first dose + 1

Duration of exposure (months) = (date of last dose +14 – date of first dose + 1) / 30.4375

Planned number of dosing = duration of drug exposure (days) / 14

Planned total dose (mg) = weight at baseline (kg) × 3 mg/kg × planned number of dosing

SHR-1210-Q3W group:

Duration of exposure (days) = date of last dose +21 – date of first dose + 1.

Duration of exposure (months) = (date of last dose +21 – date of first dose + 1) / 30.44.

Planned number of dosing = duration of drug exposure (day) / 21

Planned total dose (mg) = weight at baseline (kg) × 3 mg/kg × planned number of dosing

Cumulative dose (mg) = total dose during drug exposure

Dose intensity (mg/month) = cumulative dose/duration of drug exposure (months)

Compliance (%) = (cumulative dose/planned total dose) × 100%

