7 DOSE ADJUSTMENT AND SAFETY MANAGEMENT

7.1 Dose Level and Regimen

The dose level in trial is 3 mg/kg, q2w or q3w, intravenously infusion over 30 minutes (no less than 20 minutes and no more than 60 minutes, including a wash-out period), until progression of disease, unacceptable toxicity, withdrawal of informed consent or the end of study, whichever comes first.

The administration interval cannot be less than 12 days at the frequency of once every two weeks. The administration interval cannot be less than 18 days at the frequency of once every three weeks. Dosing 3 days post the intended date of administration will be considered as delayed dose. The subsequent time of administration will be calculated on the actual date of the previous dose.

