7.2.3 Criteria for dose resumption

When treatment-related AEs recover to \leq Grade 1 or baseline level, the dose can be resumed, except the following:

- The therapy can be resumed for the subjects with Grade 2 fatigue that has not been recovered;
- The therapy can be continued for Grade 2 cutaneous AE;
- For subjects with AST, ALT or TBIL Grade 1 elevation at baseline who delay SHR-1210 for reasons other than treatment-related hepatic AE, the therapy can be resumed in the presence of AST, ALT or TBIL Grade 2 elevations;
- For subjects who delay the dose for treatment-related AST, ALT or TBIL elevation, when these parameters are recovered to baseline CTCAE Grade or normal (see Section 7.2.4) and have not reached the criteria for permanent discontinuation of the treatment, the investigational drugs can be resumed;
- In the case that the treatment-related endocrine disorder can be sufficiently controlled only with hormone replacement at physiological dose, the treatment can be resumed.

The study medication is allowed to be delayed for up to 6 weeks, as calculated from the last dose. If the subject still does not reach the criteria for dose resumption after delay for 6 weeks, the study treatment need to be discontinued permanently, except the exceptions mentioned in Section 7.2.4. The guideline on management of adverse reactions is seen in Appendix 4 in detail.

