 - After the use of cortisol for management of treatment-related AEs, the study medication is allowed to be delayed for > 6 weeks due to the need for dose tapering. Discussion with the sponsor must be made before resuming the dose. During the dose delay, the tumor assessment should continue as required by the protocol. Safety visits and laboratory tests should also be performed at the original frequency (at least once every 6 weeks, window period \pm 7 days) or more frequently when clinically indicated;
 - The dose delay for > 6 weeks due to non-related reasons must be discussed with the sponsor prior to resuming administration. During dose delay, the tumor evaluation should still proceed as required in the protocol. Safety visits and laboratory examinations should also be performed at the original frequency (at least once every 6 weeks, window period \pm 7 days), or more frequently when clinically indicated;
- Clinical AE, laboratory abnormality, or complications may bring major risk to subjects who continue taking the study medication, as judged by investigators.
- Progression of disease evaluated by investigators in accordance with RECIST v1.1 (unless the subject meets the criteria in Section 3.2.4).

Even though the study medication is terminated, subjects must continue to perform tumor evaluation as required in the protocol.

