5.2.5. Protocol deviations

Before the database is locked, all subjects' data on the CRF will be checked for important protocol deviations. All possible critical or major protocol deviations will be evaluated by the investigator and the sponsor.

All critical or major protocol deviations will be summarized and described by types, and analyzed in listing.

Critical or major protocol deviations include, but are not limited to:

- Serious violation of the eligibility criteria;
- Wrong assignment into treatment groups;
- Use of prohibited drug during treatment;
- Poor compliance (compliance rate < 50%).

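### Compliance is measured against elapsed time, so long or repeated holds that the protocol requires or permits can push a subject with few doses below the 50% major-deviation limit

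*SAP*

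**What the plan says.** **SAP 5.1.3** measures Q2W exposure as "Duration of exposure (days) = date of last dose + 14 – date of first dose + 1" and Q3W exposure as "Duration of exposure (days) = date of last dose +21 – date of first dose + 1". It divides by the dosing interval to get planned doses (for Q2W, "Planned number of dosing = duration of drug exposure (days) / 14"), multiplies by 3 mg/kg and baseline weight, and defines compliance as cumulative mg over planned mg. It makes no allowance for holds.

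**SAP 5.2.5** includes in its critical or major deviations "Poor compliance (compliance rate < 50" (in per cent), again with no exception for holds. Such deviations are summarised and listed.

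**SAP 5.1.1** says of the per-protocol set: "The PPS forms by excluding subjects with protocol deviation that has important effect on the study results from the FAS". Table 1 there uses the PPS for ORR, DCR and the 6/9/12-month OS rates.

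**The protocol** treats a hold as part of the plan:
- Section 7.1: "The subsequent time of administration will be calculated on the actual date of the previous dose".
- Section 7.2.1 rules out dose modification, and 7.2.2 lists toxicities for which the dose is to be delayed.
- Section 7.2.3: "The study medication is allowed to be delayed for up to 6 weeks, as calculated from the last dose".
- Section 7.2.4 makes two exceptions to that limit. After steroids for a treatment-related AE, "the study medication is allowed to be delayed for > 6 weeks due to the need for dose tapering". A longer delay for unrelated reasons is also possible after discussion with the sponsor.

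**The concern.** Under protocol 7.1 a held dose is not overdue, because the calendar restarts from the dose actually given. The SAP formula counts it as planned and missed. Dose levels are fixed and the exposure span ends one interval after the last dose, so gaps between doses are the main way compliance can fall far below 100%. The ratio behaves as a relative dose intensity but is used to judge adherence to the protocol.

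Two things are at stake. First, a subject managed exactly as sections 7.2.2 to 7.2.4 direct can be labelled a major deviator, and protocol section 16 carries major violations into the trial report. Second, that subject becomes a candidate for exclusion from the PPS. Any such exclusion would depend on toxicity during treatment, and would depend on the schedule because the same gap costs a Q2W subject more than a Q3W subject.

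Long holds are foreseeable. For hepatic events, protocol 7.3.2 describes a steroid reduction lasting at least a month, and 7.2.4 anticipates holds beyond 6 weeks for tapering.

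**Working it through.** The documents give formulas and a cut-off but no computed compliance figure, so there is nothing to reproduce.

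**Assumptions.** Every infusion is complete and at baseline weight. The 6-week limit is read as 42 days between consecutive doses.

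**Formula.** For *n* doses with mean gap *L* days and interval τ (14 or 21), SAP 5.1.3 gives

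compliance = nτ / (L(n − 1) + τ + 1).

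**Every gap 42 days**

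| Doses | Q2W | Q2W without the extra day | Q3W |
|---|---|---|---|
| 2 | 28/57 = 49.1% | 28/56 = 50.0% | 42/64 = 65.6% |
| 3 | 42/99 = 42.4% | 42/98 = 42.9% | 63/106 = 59.4% |
| 4 | 56/141 = 39.7% | 56/140 = 40.0% | 84/148 = 56.8% |

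For Q3W the general value is 21n/(42n − 20). Half the denominator is 21n − 10, which is less than 21n, so the ratio always exceeds 50%. Under these assumptions no Q3W subject is flagged while all gaps are at most 42 days.

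**One 42-day gap, other doses on time (Q2W).** Compliance = 14n/(14n + 29): 49.1% with 2 doses, 59.2% with 3, 74.3% with 6, 85.3% with 12. Only the two-dose subject is flagged, and only because of the extra day.

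**Mean gap needed to flag Q2W.** Setting the formula below one half gives L > (28n − 15)/(n − 1): more than 41 days with 2 doses, 34.5 with 3, 30.6 with 6 and 29.2 with 12, tending to 28.

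**One 70-day gap, other doses on time** (illustrating the exceptions in 7.2.4)
- Q2W, 14n/(14n + 57): 3 doses 42/99 = 42.4%; 4 doses 56/113 = 49.6%, or 56/112 = 50.0% without the extra day.
- Q3W, 21n/(21n + 50): 2 doses 42/92 = 45.7%; 3 doses 63/113 = 55.8%.

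**Relaxing the full-dose assumption.** Compliance is in mg. One full Q3W dose and one infusion stopped at 30% (an illustrative fraction), 42 days apart, give 1.3 × 21/64 = 42.7%. The documents do not say whether later doses use current weight. If they do, dosing weight 10% or 5% below baseline with every gap at 42 days takes Q3W below 50% from 5 or 10 doses.

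**Early stopping.** A single Q2W dose scores 14/15 = 93.3% whatever the reason for stopping, because time after the last dose is capped at one interval.

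**The case against.** The strongest reply is that this is a corner case with no effect on a primary conclusion. Much of that stands.

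- *A reader might infer that any protocol-required hold counts as poor compliance.* It does not. One 42-day gap leaves a Q2W subject at 59.2% with three doses and 74.3% with six. Long or repeated holds with few doses are needed, or a mean gap of roughly twice the planned one.
- *A reader might infer that only Q2W subjects can ever be flagged.* That holds only with full doses at baseline weight and all gaps within 42 days. The exceptions in protocol 7.2.4 and partial infusions (protocol 6.6.1 provides for stopping an infusion) bring Q3W within reach.
- *A reader might infer that the flag removes the subject from the PPS.* SAP 5.1.1 excludes only deviations with an important effect on results, decided by the medical and statistical teams before lock. Protocol 11.2 and SAP 5.2.5 provide for review by the sponsor and investigators. That review can retain a subject held for toxicity. The PPS is supportive, the FAS is primary, and SAP section 3 judges effectiveness on overall confidence intervals.
- *Some examples depend on the extra day.* Two Q2W doses 42 days apart, and four with one 70-day gap, become exactly 50.0% without it and are then not flagged. The three-dose case does not depend on it (42.9%).
- *A remedy based on reasons for delay needs a recorded reason.* Protocol 6.4 and SAP 5.3 mention dates and doses, and AE actions taken (protocol 9.1.1) cover only AE-driven holds. Investigator-judged delays and delays for unrelated reasons could exempt nearly every gap unless documentation is required.

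None of this removes the mismatch. SAP 5.2.5 states no exception, and relying on reviewers to overrule a listed criterion case by case is weaker than defining it correctly.

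**Conclusion.** The point holds in a limited form. As written, SAP 5.1.3 and 5.2.5 can label a subject a major deviator for following protocol 7.2.2 to 7.2.4. The clearest case is three Q2W doses at 42-day gaps: 42.4%, or 42.9% without the extra day, against 59.4% for Q3W on the same dates. The contrast between schedules rests on full doses at baseline weight and gaps of at most 42 days. Beyond 42 days Q3W can also be flagged (45.7% for two doses 70 days apart).

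The documents give no expected frequency of such holds, so the number of subjects affected cannot be estimated. They do not support the reading that holds are generally scored as poor compliance, or that the efficacy conclusion is biased. The consequence is a false deviation label and a possible toxicity-dependent and schedule-dependent exclusion from a supportive analysis. That justifies a correction before database lock.

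**What to change.** In SAP 5.1.3, keep the elapsed-time ratio and report it as a dose-intensity summary. For the 50% criterion in SAP 5.2.5, use a planned count that leaves out intervals documented as holds under protocol 7.2.2 to 7.2.4. One way is to subtract from exposure days, for each documented hold, the days beyond the planned interval before dividing by 14 or 21. For three doses at 42-day gaps this gives:
- Q2W: 99 − 2 × 28 = 43 days, so 42/43 = 97.7%.
- Q3W: 106 − 2 × 21 = 64 days, so 63/64 = 98.4%.

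These equal the formula's values for three doses given on schedule. State in 5.2.5 that such a hold alone is neither a major deviation nor a reason for exclusion from the PPS. Gaps without documentation stay in the planned count, so the criterion can still detect missed doses.

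The cost is SAP wording and one derivation. Each long gap must be classified, from the AE actions-taken record or, for other holds, from the documented reason or sponsor discussion. No clinical rule changes. Partial infusions would still lower the ratio, and early stopping would still go undetected.
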